Research program

Vacuum-formed retainer versus bonded cuspid-to-cuspid retainer to prevent relapse after orthodontic treatment– A randomized controlled trial about stability and patients' perceptions

NCT03070444

PhD student [name], Senior consultant, Department of orthodontics, Gävle

Supervisor: [name], Associate professor, PhD, Department of oral and maxillofacial surgery, Umeå University

Assistant supervisor: [name], Senior consultant, Department of orthodontics, Gävle

Assistant supervisor: [name], Associate professor, Department of oral and maxillofacial surgery, Umeå University

Aim

The overall objective of this randomized trial is to evaluate and compare stability after orthodontic treatment with an Essix retainer and a bonded cuspid-to-cuspid retainer (CTC) respectively in the mandibular arch and longitudinally follow these patients over time up to 5 years. The patients' perceptions of the two methods are also evaluated with questionnaires during the follow-up period.

A further aim of this study is to analyze the relationship between diagnosis, treatment outcome, treatment time, age at start of treatment and stability with an Essix-retainer in the maxilla.

Introduction

For successful orthodontic treatment the teeth need to be maintained in their corrected position after removal of orthodontic appliances. According to Proffit (2012) orthodontic treatment results are potentially unstable and therefore retention is necessary for three major reasons: the gingival and periodontal tissues require time for reorganization, growth changes can cause relapse and pressure from soft tissues i.e tongue, lips and cheeks can cause the teeth to move or rotate in an unwanted direction.

To prevent relapse patients are provided with fixed or removable retainers. The advantage of fixed retainers is that they are bonded to the palatal or lingual surfaces and do not depend on the patient's compliance. On the other hand these retainers demand good oral hygiene procedures to avoid plaque and calculus accumulation and the bonding procedure is time consuming and technique sensitive (Dahl and Zachrisson, 1991).

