Only a few studies have analyzed patients' perception of orthodontic treatment (Bennett et al 1999, Hichens 2007, Feldmann et al 2012). Very few studies have analyzed patients' perception of retention appliances. Kumar and Bansal (2011) compared in a prospective study the effectiveness and acceptability of Essix and Begg retainers. They found that both appliances allowed some relapse but the differences were small and not clinically significant. The patients liked the comfort and appearance of the Essix retainer and preferred the Begg retainer for chewing and biting.

Although retention is a decisive factor for successful orthodontic treatment there are no evidence-based recommendations in the literature for retention appliances considering diagnoses before treatment such as vertical and skeletal deviations, the type of orthodontic movement (e.g. expansion or extraction cases) or for patients treated with fixed appliances and orthognathic surgery. Especially for patients with orthognathic surgery the choice of retention method and prevention of relapse are crucial since both skeletal and dental changes occur during treatment.

Materials and methods

The study is conducted at the Orthodontic Clinic, Gävle, Sweden and consists of 104 patients. All patients are treated with fixed appliances in the upper and lower jaw (standard .022 straight wire), both with and without extractions.

Patients treated with Rapid Maxillary Expansion (RME), orthognathic surgery, segmented appliance and patients with syndromes or agenesis of a mandibular incisor were excluded from the trial.

All patients who meet the inclusion criteria are invited to enter the trial. One experienced orthodontist (AK) provides the patients and parents with both oral and written information about the study protocol. After written consent is obtained from both the patient and parent the patients are randomized in blocks and stratified by gender into two groups. The allocation sequence is computer generated by a statistician at Gävleborg Count Hospital and concealed in opaque envelopes until randomization.

The patients are randomized into two groups with 52 patients in each group. All patients have Essix retainers in the maxilla covering all erupted teeth. The extension of the Essix retainers in the mandible covers only the dentition from first premolar to first premolar. The CTC-retainer is bonded to lingual surfaces of the mandibular canines.

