Patients with rotated lower incisors (more than 30 degree) are treated with circumferential supracrestal fiberotomy 2 weeks prior to retention.

Group A: Retention with a CTC in the mandible and Essix retainer in the maxilla.

Two weeks before debonding an impression of the mandibular jaw is taken in order to manufacture the CTC retainer. The CTC-retainer is bonded to the canines directly after debonding. The Essix retainer is manufactured on dental casts after debonding and handed out to the patients the same day. The patients are instructed to wear the Essix retainer full-time the first week and thereafter night only.

Group B: Retention with Essix retainers in the maxilla and mandible.

The Essix retainers are manufactured on dental casts after debonding and handed out to the patients the same day. The patients are instructed to wear the Essix retainers full-time the first week and thereafter night only.

Dental cast are obtained at the debond appointment (T1) and at the follow-up controls after six months (T2), 18 months (T3) and 5 years (T4) for both groups. All measurements on casts are made with an electronic digital calliper to the nearest 0.25 mm. Comparisons within and between groups are performed.

Stability after retention is also analyzed depending on diagnoses before treatment and treatment outcome.

Outcome measures on the dental casts are as follow:

- Little's irregularity index
- Intercanine width
- Intermolar width
- Arch length
- Overjet
- Overbite

To assess measurement precision and reliability, 30 randomly selected dental casts are measured by the same examiner at a five weeks interval.

At the visit two weeks in retention and at the follow-up visits after 6, 18 and 60 months the patients assessed questionnaires in order to evaluate their experience of retention with an Essix retainer and a CTC respectively. The questionnaires include self-report questions from a previous study where reliability and face validity were found to be acceptable (Feldmann et al 2007). In addition, a few questions modified for this study are included. The fit of the retainers and the CTC are checked at each visit. All questionnaires are evaluated and compared between the two groups

Statistical analysis

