Descriptive statistics are calculated for both groups (median, interquartile ranges, and test for normal distribution). The post-treatment changes are described by comparing measurements at debond (T1), after 6 months (T2), after 18 months (T3), and after 5 years (T4). Generalized estimating equations (GEE) are used to estimate the effect of the two treatment groups over time for the outcome variables. In the GEE analysis, all digital measurements, extraction therapy, sex, retention group, and time and the interaction of time with retention group are tested as explanatory variables (predictors). The GEE correlation structure is set to autoregressive, a convenient option for models with time-dependent observations.

Mann-Whitney U tests are used to analyse and compare the answers on questionnaires for the VFR/VFR and VFR/CTC group. Spearman's correlation coefficient is calculated to determine the relationship between patients' perceptions, self-reported VFR compliance, and LII. Demographic data are analysed with cross tabulations. P-values less than 0.05 are considered statistically significant.

Ethical considerations

All patients and parents are given oral and written information and sign a written consent before being included in the trial. The participation is voluntary and patients can leave the trial at any time without giving reasons.

Both of the tested retention-appliances are common and used frequently in orthodontic practices. The impressions at the follow-up visits are additional for this study.

The Ethics Committee of Uppsala (Regionala etikprövningsnämnden) approved the study protocol (diarienummer: 2009/177).

Research projects:

1. Effectiveness of Essix retainer versus bonded CTC in the mandibular arch after 6 and 18 months.

Aim: The aim of this project is to evaluate and compare stability in the mandibular arch 6 and 18 months after retention with an Essix retainer compared to retention with a bonded cuspid-to-cuspid retainer (CTC).

Material and methods: 104 patient are randomized into 2 groups; CTC (group A) and Essix retainer (group B). Little's Irregularity Index, intercanine width, intermolar width, arch length, overjet and overbite are measured on dental casts and analysed at the debond appointment, after 6 months and after 18 months.

The null hypothesis is that there is no difference in retention capacity between Essix retainer and cuspid-to-cuspid retainer.

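### Does the Spearman analysis of retainer wear and irregularity need an arm named, given that one group wears no vacuum-formed retainer in the lower jaw?

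*Combined protocol and SAP*

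**What the plan says.** The Statistical analysis section names both retention groups for the Mann-Whitney comparison of questionnaire answers. The next sentence plans Spearman correlations among "perceptions, self-reported VFR compliance, and LII" and names no group, jaw or visit. It also does not say whether LII is taken as a level or as a change from debond (T1).

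Materials and methods describes who wears what:

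- Upper jaw, both groups: "All patients have Essix retainers in the maxilla covering all erupted teeth".
- Group A: "Group A: Retention with a CTC in the mandible and Essix retainer in the maxilla". On the fixed retainer: "The CTC-retainer is bonded to lingual surfaces of the mandibular canines".
- Group B has vacuum-formed retainers (VFR, called Essix in most of the text) in both jaws. On the lower one: "The extension of the Essix retainers in the mandible covers only the dentition from first premolar to first premolar".

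Questionnaire timing is given as "At the visit two weeks in retention and at the follow-up visits after 6, 18 and 60 months the patients assessed questionnaires". Casts are taken at debond, 6 months, 18 months and 5 years. After the cast measurements the same section adds: "Comparisons within and between groups are performed".

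The Introduction describes fixed retainers as "bonded to the palatal or lingual surfaces and do not depend on the patient's compliance".

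**The concern.** LII is a lower-jaw score here. The title of its cited source says so, the two lower-arch projects (1 and 3) list it, and the upper-jaw project (4) leaves it out. In group A, VFR wear therefore concerns the opposite jaw from the one scored. In group B it can include the appliance that covers the scored teeth. Every patient has an upper VFR, so all 104 could report wear, and pooling is a natural reading of a sentence that names no arm.

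The Introduction's remark on compliance gives a reason to expect a weaker relation in group A. A pooled coefficient would then understate the relation in group B. Compliance is not among the listed predictors of the generalized estimating equations (GEE), so this is the only planned analysis that sets reported wear beside stability. A small pooled value could be misread as showing that wear hardly matters.

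**Working it through.** **1. What the text settles.** The documents give no correlation, effect size or power figure, so there is no plan figure to reproduce. The sentence neither requires nor excludes pooling. The statement that comparisons are made within and between groups follows the cast measurements. It does not define the correlation, but it shows that by-arm work is part of the plan. The compliance item is not reproduced. If it asks about each jaw and the lower-jaw answer is used, group A has no value and pooling cannot occur.

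**2. Size of dilution if the arms were pooled.** Inputs are 52 per arm (Materials and methods) and two-sided 5% (the plan gives 0.05 without sidedness). The within-arm correlations are assumed, with bivariate normal data and no difference between arms in level or spread. For a normal correlation r, Spearman's value is (6/π)·arcsin(r/2). With equal arms and equal distributions of each variable, the pooled value is the mean of the two arms' values.

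- Group B, r = -0.4: (6/π)·arcsin(-0.2) = -0.385.
- Group A, r = 0: pooled = (0 - 0.385)/2 = -0.19.
- Group A, r = -0.2: (6/π)·arcsin(-0.1) = -0.191; pooled = (-0.191 - 0.385)/2 = -0.29.

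Simulation of 20,000 trials per row, with group B at -0.4, agrees to within about 0.01:

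| Assumed r in group A | Pooled rho | Group B rho | Power, pooled | Power, group B |
|---|---|---|---|---|
| 0 | -0.19 | -0.38 | 49% | about 80% |
| -0.1 | -0.24 | -0.38 | 69% | about 80% |
| -0.2 | -0.28 | -0.38 | 84% | about 80% |
| -0.4 | -0.38 | -0.38 | 98% | about 80% |

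A separate run of 6,000 trials for the first row gave -0.19 with 50% power pooled, and -0.38 with 81% in group B. The pooled value is half of group B's only in that row, where group A's correlation is zero.

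**3. Where pooling stops costing power.** The smallest correlation detectable with 80% power is tanh[(1.960 + 0.842)·√(1/(n - 3))].

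- n = 52: tanh(2.802/7) = 0.38.
- n = 104: tanh(2.802/√101) = 0.27.

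The ratio is 0.272/0.380 = 0.716. Pooling breaks even when (A + B)/2 = 0.716·B, that is A = (2 × 0.716 - 1)·B = 0.43·B. Below that, group B alone has more power; above it, pooling does.

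**4. Confounding by arm.** A spurious pooled correlation requires both compliance and LII to differ by arm. With no within-arm relation, assumed shifts of 0.3, 0.5 and 0.8 SD on both variables give false-positive rates of 5.5%, 9% and 28%. If only one variable shifts, the rate stays at 5%. The documents report no such shifts, and the VFR wear instructions are the same in both arms.

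**5. What depends on the result.** The null hypotheses under Research projects concern retention capacity in the lower arch, patients' perception, and upper-jaw stability by diagnosis, outcome, treatment time and age. None uses this correlation. The GEE and Mann-Whitney comparisons are not affected.

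**The case for a change.** The strongest case for a change is that the choice of arm is left open until data are seen, in an analysis where the design itself makes arm matter. The section names the groups in one sentence and drops them in the next. It applies the 0.05 threshold without calling the correlation exploratory. The two-week questionnaire has no cast at the same visit, so several pairings are possible. A few sentences would settle all of this with the same data.

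The omissions stand: arm, jaw of the compliance item, visit and form of LII are all unstated. The reason to expect different relations by arm is also sound, although the Introduction's remark is general and gives no size.

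The step from omission to error does not stand. The halving needs a group A correlation near zero. No document shows this, and it is not assured, because the fixed retainer is bonded to the canines only. Much of the obvious remedy is preference. Change from T1 rather than level is not dictated by the plan. Making group B the main result gives up power if group A's correlation is about half of group B's or more (80% against 84% at half, 81% against 98% if equal, at -0.4 in group B). An arm-adjusted pooled coefficient removes confounding but not dilution: with group A at zero it is still -0.19, with 49% power.

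**Conclusion.** No change follows. The plan leaves a secondary correlation briefly described, but it states no rule or figure that is wrong. An analyst who knows that group A has no lower VFR can run it by arm within the present wording. Pooling would understate group B's association whenever group A's is weaker: by about half if group A's correlation is zero, and by about a quarter (-0.28 against -0.38) if it is half of group B's. In the second case pooling also has slightly more power. These sizes rest on assumed correlations, 52 complete patients per arm, normal data and no arm shifts. The trial's documents support none of the correlations in particular.

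The randomised comparison, the questionnaire comparison and every stated null hypothesis are untouched. Compliance is self-reported and not randomised, so even a clean group B coefficient would show association only. A pooled coefficient presented without the arm values should be read with that and the dilution in mind.

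### Projects 1 and 3 each test one null on six unranked cast outcomes at unadjusted 0.05, with no primary outcome, deciding contrast or combining rule

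*Combined protocol and SAP*

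**What the plan says.** Under Materials and methods, the line "Outcome measures on the dental casts are as follow" introduces a flat list: LII, intercanine width, intermolar width, arch length, overjet and overbite. None is called primary.

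Research project 1 aims to "evaluate and compare stability in the mandibular arch 6 and 18 months after retention with an Essix retainer", compared with the bonded retainer. After LII, its measures are given as "intercanine width, intermolar width, arch length, overjet and overbite are measured on dental casts and analysed at the debond appointment, after 6 months"; the 18-month visit is listed on the same footing. Its null reads: "The null hypothesis is that there is no difference in retention capacity between Essix retainer and cuspid-to-cuspid retainer". Project 3 repeats that null and the same six measures, at 5 years only.

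The Statistical analysis section says: "Generalized estimating equations (GEE) are used to estimate the effect of the two treatment groups over time for the outcome variables". On the model terms it says: "In the GEE analysis, all digital measurements, extraction therapy, sex, retention group, and time and the interaction of time with retention group are tested". The significance rule is "P-values less than 0.05 are considered statistically significant", with no multiplicity procedure.

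The one place LII stands apart from the other cast measures is the Spearman analysis, which relates patients' perceptions, "self-reported VFR compliance, and LII". That does not make it primary. The sample size of 104 (52 per group) comes without an effect size, SD or power, so no primary outcome can be inferred from it.

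**The concern.** Each project has one null but six ways to reject it, and in project 1 two visits for each. The plan does not say which result counts. A claim that one retainer holds better could rest on whichever measure falls below 0.05. Two analysts following the same text could differ, one rejecting the null and the other not.

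The contrast is open in two further ways. First, the group, time and interaction terms are all tested, and none is named as the deciding one. Second, the digital measurements are listed among the predictors, so the model for LII may or may not contain the other five cast measures. At follow-up those are themselves post-randomisation outcomes, and adjusting for them changes what the group effect on LII means.

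**Working it through.** **Inputs from the documents:** six cast outcomes; two post-debond visits in project 1 (6 and 18 months) and one in project 3 (5 years); threshold 0.05; 52 per arm; an autoregressive GEE structure.

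**Assumed:** two-sided tests (the nulls are of no difference); any one significant outcome rejects the null; equal correlation r between the outcomes' test statistics; 80% power; no dropout. The documents give no correlations, so a range is shown. The plan has no figure of its own to reproduce beyond 52 + 52 = 104.

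**1. One test per outcome, per project.** With independent outcomes the chance of at least one p < 0.05 is 1 − 0.95^6 = 26.5%. Correlated cases come from simulated normal test statistics:

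| r | six tests at 0.05 | six tests at 0.05/6 |
|---|---|---|
| 0 | 26% | 4.9% |
| 0.3 | 24% | 4.6% |
| 0.5 | 21% | 4.1% |
| 0.7 | 16% | 3.3% |
| 0.9 | 11% | 2.1% |

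**2. Side case: project 1 with both visits tested separately (12 tests).** The changes T2 − T1 and T3 − T1 share T1. Under AR(1) by visit order with equal variances, their correlation is (1 − ρ²)/√[2(1 − ρ) × 2(1 − ρ²)] = √(1 + ρ)/2, which runs from 0.50 to 0.71. Simulated risk of at least one p < 0.05:

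| r | visit correlation 0.50 | visit correlation 0.71 |
|---|---|---|
| 0 | 43.4% | 40.6% |
| 0.5 | 34.9% | 32.2% |
| 0.7 | 28.1% | 25.7% |
| 0.9 | 19.0% | 17.3% |

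At 0.05/12 the risk is 2.0–4.7%.

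**3. One LII contrast per project.** Each is nominally 5%. A GEE simulation with 104 patients, four visits, AR(1) with ρ = 0.7, robust standard errors and 2,000 runs gave 4.6–6.1%. The 18-month and 5-year changes correlate 0.50–0.82 under the same AR(1) reasoning. At least one false LII claim over both projects then has probability 9.1–7.7%.

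**4. Detectable difference at 52 per arm.** Formula: (z for the two-sided level + 0.842) × √(2/52), where √(2/52) = 0.196.
- At 0.05: (1.960 + 0.842) × 0.196 = 0.55 SD.
- At 0.05/6: 0.68 SD.
- At 0.05/12: 0.73 SD.

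Power at 0.55 SD falls from 80% to 56.5% at 0.05/6 and 47.5% at 0.05/12.

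**5. Other cast measures as predictors of LII.** Suppose all six measures truly differ by 0.5 SD. With the other five in the model, the LII contrast becomes 0.5 × (1 − r)/(1 + 4r).
- r = 0.3: 0.5 × 0.7/2.2 = 0.16 SD.
- r = 0.5: 0.5 × 0.5/3 = 0.08 SD.

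The GEE simulation gave 0.16 and 0.09. If LII does not differ but the other five do by 0.5 SD, LII was declared different in 48–77% of runs over the same range of r.

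**The case against.** The strongest reply is that the error rates describe a rule the plan never states. If all six outcomes had to be significant, type I error would not rise; power would fall instead. That is right, and it is why the figures are conditional. It does not rescue the plan, because no rule is given.

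Several narrower points also have weight.
- Separate testing at 6 and 18 months is not described. One overall interaction test per outcome would give six tests, so the 12-test figures are secondary.
- Equal variance over visits is doubtful for LII, since T1 directly follows active correction. If the T1 SD were half the later SD (an assumption), the visit correlation could be about 0.20–0.90, and the 12-test risk about 35–45% at r = 0 and 22–30% at r = 0.7. The range widens; the inflation remains.
- The term for digital measurements is undefined and could mean debond values. The false-claim figures for that model depend on the set-up: with the effect at one visit only, they were about 36% at r = 0.3 and 68% at r = 0.5. The direction is firm; the size is not.
- LII and 18 months are choices the text does not dictate.

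It could also be said that LII is plainly primary, or that the trial is exploratory. If the first is so, one sentence would settle it. The second sits badly with stated null hypotheses, a significance threshold and the hope under Relevance of informing how retention is planned.

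**Conclusion.** The concern holds. Projects 1 and 3 name no primary outcome, deciding contrast or combining rule, and project 1 does not rank its visits; project 3 does fix one. If any significant outcome rejects the null, the false-claim risk is about 11–26% per project with one test per outcome, roughly two to five times the nominal 5%. In project 1 it is about 26–43% (r from 0.7 to 0) if both visits are tested separately, and 17–19% at r = 0.9. These figures rest on assumed outcome correlations; the 12-test figures also assume AR(1) and equal variances. The gap itself rests on the text alone. The SAP should be amended. The trial's conduct is not affected.

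**What to change.** Before outcome data are examined, name one primary outcome and one contrast per project. If data have already been seen, date and disclose the change.

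- **Outcome and contrast.** LII is a natural option: it heads the list and is the only cast measure in the Spearman analysis. The contrast would be the between-arm difference in change from debond, at 18 months (the later project 1 visit) and at 5 years (project 3), each two-sided at 0.05. Another outcome or visit would serve if named in advance.
- **Model.** GEE with group, categorical visit (T1 as reference), group-by-visit, sex and extraction therapy only. Leave the other cast measures out.
- **Secondary results.** Report with 95% CIs and Holm adjustment within project: 11 tests in project 1 (five measures at 18 months plus six at 6 months) and five in project 3. State that they do not decide the null. With a separate 0.05 for this family, the chance of any false claim in a project is bounded by 0.05 + 0.05 = 10%.
- **Alternative.** If all six are to stay co-primary, test each at 0.05/6 at one named visit, or at 0.05/12 in project 1 if both visits count.

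Project 2's own null is outside this change.

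**Cost.** SAP wording only; patients and data collection are unaffected. The other five measures and the 6-month visit lose any stand-alone unadjusted claim. The LII option keeps the detectable difference at 0.55 SD, a best case because it allows for no dropout. The co-primary option raises it to 0.68 or 0.73 SD.
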